10.4.2.1.3 Hypothesis

STAGE-12 will result in a greater increase on measures of spirituality than TAU.

The outcome variable will be a measure of spirituality as assessed by the Spiritual Involvement and Beliefs Scale at baseline and week 8/end of treatment. The data will be analyzed using a hierarchical linear model similar to the model for the primary outcome. Let α_{SP} denote the effect of the STAGE-12 treatment in the Level-2 model. The hypotheses H₀: α_{SP} =0 vs. H₁: α_{SP} ≠0 will be evaluated and rejection of the null hypothesis with α_{SP} > 0 would indicate that STAGE-12 treatment results a greater increase on measures of spirituality than TAU.

10.4.2.1.4 Hypothesis

STAGE-12 will result in a greater reduction in 12-step perceived barriers to 12-step involvement than TAU.

The outcome variable will be a measure of perceived barriers to 12-step involvement as assessed by the Perceived Barriers subscale of the Survey of Readiness at baseline and week 8/end of treatment. The data will be analyzed using a hierarchical linear model similar to the model for the primary outcome. Let α_{PBAR} denote the effect of the STAGE-12 treatment in the Level-2 model. The hypotheses H₀: α_{PBAR} =0 vs. H₁: $\alpha_{PBAR} \neq 0$ will be evaluated and rejection of the null hypothesis with

 α_{PBAR} < 0 would indicate that STAGE-12 treatment results a greater reduction on measures of 12-step ambivalence than TAU.

10.4.3 Mediation

10.4.3.1 Objective

[figure not shown]
To examine 12-step meeting attendance and involvement as mediators of substance use outcomes.

10.4.3.1.1 Hypothesis

Reductions in substance use, regardless of treatment condition, are mediated by increases in 12-step attendance and 12-step activities.

The outcome variable will be percent of days of substance use over the assessment window, based on Substance Use Calendar alone and assessed at baseline, weeks 4, 8/end of treatment, 3 months and 6 months. The hypothesis will be investigated by adding an interaction term time*Mediator to the hierarchical linear model for the primary outcome, where Mediator denotes the factor of interest (12-step attendance or 12-step activities). Let γ_M denote the model coefficient associated with the time*Mediator term. The hypothesis H_0 : γ_M =0 vs. H_1 : $\gamma_M \neq 0$ will be evaluated and rejection of the null hypothesis with γ_M < 0 would indicate that increases in 12-step attendance (12-step activities) result in reduction in substance use, regardless of treatment condition.

Objective: To examine client attitudes and beliefs as mediators of 12-step meeting attendance and involvement.

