treatment approach for stimulant abusers. Specifically, the present approach is based on the TSF therapy from Project MATCH as modified for use with drug abusers (Baker 1998) and as delivered in a group format (Brown, Seraganian et al. 2002; Brown, Seraganian et al. 2002). These group sessions will be augmented further by three individual sessions, two of which are drawn from the TSF manual, into which are integrated action-oriented interventions derived from the intensive referral procedure of Timko, et al. (Timko, DeBenedetti et al., 2006) as a means of increasing involvement in 12-step activities and meeting attendance. This combined group plus individual approach has been named STAGE-12 (STimulant Abuser Groups to Engage in 12-Step). The study will examine the extent to which this approach, integrated into treatment as usual, will lead to significantly greater reductions in stimulant use compared to treatment as usual (TAU). It will also examine the extent to which STAGE-12 increases involvement and meeting attendance over and above that of clients receiving TAU. The extent to which increases in 12-step involvement and attendance mediate reductions in subsequent substance use also will be examined.

Twelve-step programs serve as cost-effective resources that complement, support, and extend the cognitive and behavioral changes made in treatment (McCrady 1994). However, given the low rates of involvement in and high rates of attrition from 12-step programs, it is necessary to evaluate methods to help substance abusers and treatment programs take full advantage of self-help groups (Humphreys 1999). Implementation of systematic, structured, and manual-guided 12-step programs, integrated within treatment, represents one such method to increase engagement and retention in professional treatment. The proposed project responds to a topic identified by the CTN's CTP Caucus and CTP staff (Forman, Bovasso et al. 2001) as a high priority for investigation in the CTN, namely facilitating12-step involvement. If successful, this structured, manual-guided intervention would augment the more general 12-step orientation characterizing many community-based providers and promote better treatment outcomes.

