5.4.2.1 Substance Use Calendar

Self-reports of substance use will be assessed at each research visit via the Substance Use Calendar (SUC). Similar to the Timeline Follow-back procedure, the SUC is a calendar-based assessment in which individuals are asked to indicate whether they used cocaine, amphetamines, methamphetamines, opiates, alcohol, cannabis, or benzodiazepines on each day of the assessment period. The calendar is marked with both general (e.g., weekend days, holidays) and personal (e.g., birthday, anniversary, pay days) to help anchor the period and facilitate recall. The measure thus assesses substance use on a daily basis and allows flexible, continuous evaluation of substance use. The number of days used, either of any of the drugs or of each of them, is the variable derived from the SUC. Substance abusers' reports about their drug consumption using this method have been found to have high retest reliability, convergent and discriminate validity with other measures,

agreement with collateral informants' reports of patients' substance use, and agreement with results from urine assays (Fals-Stewart, O'Farrell, et al., 2000).

Secondary analyses will be conducted using percent of days of non-stimulant drug use and percent of days of use of any of the assessed drugs (stimulants and non-stimulants) as outcome variables. Days of 12-step meeting attendance will also be assessed using the Substance Use Calendar and will serve as one of the 12-step secondary outcome measures. Secondary measures will be collected as indicated in Table 1.

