Two modifications have been made in the measure. First, the time frame has been increased beyond one week up to a month. [name], the scale's developer, has been using a 30-day window in his ongoing research (Weiss, personal communication, 2003). The reasons for this modification include reducing the potential of an "assessment reactivity effect" and making the assessment time window comparable to that of the other measures in the protocol. The assessment window is 30-days at baseline, weeks 4 and 8, and the follow-up visits. A second modification is to ask participants how helpful they feel these behaviors have been to them during the assessment period.

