5.4.3.4 Substance-Related Measures: Predictors and Mediators

5.4.3.4.1 Short Understanding of Substance Abuse Scale (SUSS)

Humphreys and colleagues (Humphreys, Greenbaum et al. 1996) developed the Short Understanding of Substance Abuse Scale (SUSS) as a modified version of the Understanding of Alcoholism Scale. The latter scale was developed originally by Moyers and Miller (Moyers and Miller 1993) to assess alcoholics' beliefs about the etiology and treatment of alcoholism. Two changes were made. First, the scale was shortened from 50 items to 20 items. Second, the wording of the items, as well the inclusion of some new items, has been broadened to focus on both alcohol and drug use. Three factor analytically derived subscales have been identified: disease model, psychosocial model, and eclectic orientation. These subscales had Chronbach alpha coefficients of internal consistency of .78, .85, and .61 respectively. A difference between the original and modified short SUSS is that Humphreys, et al. (Humphreys, Greenbaum et al. 1996) had the measure filled out by treatment staff members, while Moyers and Miller (Moyers and Miller 1993) had the original completed by clients in treatment. The SUSS will be administered to both participants and participating counselors. This scale will be collected at baseline.

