10.4.3.1.4 Hypothesis

Increases in 12-step meeting attendance and involvement, regardless of treatment condition, are mediated by increases in disease model endorsement.

The outcome variable will be percent of days (frequency) of the behaviors addressed in the SUC, SHAQ, and ITSI over the assessment window, measured baseline, weeks 4, 8/end of treatment, 3 months and 6 months. Each of the above hypotheses will be investigated by adding an interaction term time*Mediator to the hierarchical linear model, where Mediator denotes the factor of interest. Let γ_M denote the model coefficient associated with the time*Mediator term. The hypothesis H₀: γ_M =0 vs. H₁: $\gamma_M \neq 0$ will be evaluated.

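### The mediation test in 10.4.3 reads a same-visit time-by-mediator association as cause, and hypothesis 10.4.3.1.4 cannot be tested because the SUSS is collected at baseline only

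*Protocol*

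**What the plan says.** Section 10.4.3.1.1 sets the method: "The hypothesis will be investigated by adding an interaction term time*Mediator to the hierarchical linear model for the primary outcome", where the mediator is 12-step attendance or 12-step activities. The coefficient of that term, gamma_M, is tested against zero, and a significant negative value "would indicate that increases in 12-step attendance (12-step activities) result in reduction in substance use, regardless of treatment condition".

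The outcome is percent of days of use, "based on Substance Use Calendar alone and assessed at baseline, weeks 4, 8/end of treatment, 3 months and 6 months". The mediators come from the same visits. For attendance, "Days of 12-step meeting attendance will also be assessed using the Substance Use Calendar" (5.4.2.1). For activities, the SHAQ is used, and "The assessment window is 30-days at baseline, weeks 4 and 8, and the follow-up visits" (5.4.3.2.2).

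Section 3.8 describes the aim with a time order: the extent to which involvement and attendance "mediate reductions in subsequent substance use also will be examined".

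Section 10.4.3.1.4 applies the same time-by-mediator test to three further mediators of attendance and involvement: spirituality, 12-step ambivalence and disease-model endorsement. The last hypothesis reads "Increases in 12-step meeting attendance and involvement, regardless of treatment condition, are mediated by increases in disease model endorsement". Disease-model endorsement is a subscale of the SUSS, of which 5.4.3.4.1 says "This scale will be collected at baseline". The SUSS row of Table 1 also marks baseline alone.

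**The concern.** Mediation by 12-step attendance and involvement is a listed secondary objective (4.2), and it is the mechanism on which the rationale rests. A single coefficient linking mediator and outcome from the same visit does not establish direction. Participants who use less may attend more, or a third factor such as motivation may move both. Section 3.2 makes this point about earlier literature, warning against causal inference from correlations and crediting cross-lagged and structural-equation analyses with beginning to address it. Section 10.4.3 then fixes a decision rule with a causal reading and none of that structure.

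At stake is a published statement about mechanism that the analysis cannot support, and one stated hypothesis for which the needed measurement will not exist when the trial ends.

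**Working it through.** **1. What the coefficient estimates.** With the added term, the model is in essence

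Y_ik = b0 + b1·t + b2·t·arm + gamma_M·t·M_ik [+ delta·M_ik] + random intercept and slope + error.

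The bracketed main effect is neither stated nor ruled out.

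- Without delta, t·M stands in for any association between M and Y, including one that is constant over time.
- With delta, gamma_M measures only how that association changes over time. A real but constant effect then gives gamma_M near zero.
- On neither reading is gamma_M an indirect effect. That would be a·b, with a the arm effect on the mediator and b the mediator effect on use.

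**2. Timing.** Mediator and outcome share their visits, and no lag is written. If the month-6 outcome window runs from the 3-month visit (week 13 to week 26 in 10.6), it covers 13 × 7 = 91 days. The SHAQ covers the last 30, so about 91 − 30 = 61 outcome days come before the mediator window. This applies to the SHAQ only; calendar attendance is daily.

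**3. Simulation with random intercept and slope.** Inputs from the protocol: 400 participants 1:1; weeks 0, 4, 8, 13 and 26; outcome SD 23.7 points; within-person correlation 0.5; two-sided 0.05, so the nominal rate for a significant negative result is 2.5%. Assumed: mediator SD √(14² + 14²) = 19.8 points, and every strength in the table. There were 150 trials per row. Site and court mandate are left out, and week 0 enters as an outcome row.

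| Setting | Negative gamma_M significant, no main effect | with main effect |
|---|---|---|
| Nothing related | 2.7% | 2.7% |
| Shared factor moves both trends, 5 points per SD by week 26 | 21% | 15% |
| Same, 10 points per SD | 97% | 79% |
| Same, 15 points per SD | 100% | 100% |
| Use lowers same-window attendance (0.3 per point), use trends also vary by 10 points per SD | 100% | 13% |
| Real mediation, constant effect (arm raises attendance 10 points; use falls 0.3 per point) | 100% | 2.7% |

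In all rows but the last, the mediator has no effect on use. Monte Carlo error, √(p(1−p)/150), is 1.3 percentage points at 2.7% and 3.3 at 79%.

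**4. Simulation of plain same-window correlation.** 400 participants, four post-baseline visits, compound symmetry, no effect of attendance on use. With no correlation, 2.2% of trials reject.

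- Without the main effect, a correlation of -0.1 gives 75% to 88% and -0.2 gives 100%.
- Without the main effect, a constant person-level factor explaining 5%, 10% or 20% of each variable gives 8% to 9%, 20% to 24% and 62% to 76%.
- With the main effect, these settings fall to about 2% to 3%.

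The ranges reflect differing simulation settings. One is the mediator's own correlation between visits, which the protocol does not give; the rates are lower if it is taken as zero.

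**5. Availability of the four mediators.**

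| Mediator | Instrument | Collected |
|---|---|---|
| Attendance, activities | Substance Use Calendar, SHAQ | every outcome visit |
| Spirituality | SIBS-R | baseline, week 8 |
| Ambivalence / barriers | SYRAAP | baseline, week 8 (Table 1, 10.4.2.1.4); 5.4.3.2.3 names baseline only |
| Disease-model endorsement | SUSS | baseline only |

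An increase needs two measurements. The SUSS has one.

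**The case against.** Several points on the other side stand.

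- Section 10.4.3.1.1 speaks only of adding an interaction. It does not give the full equation or say that the mediator main effect is left out. A reader might infer that the rule declares mediation for almost any same-window correlation. The documents do not support that: the high rates in step 4 arise only if the main effect is omitted, and even then a weak shared factor gives rates of 8% to 24%.
- A reader might infer that the effect of STAGE-12 on the mediators is never tested. It is, in 10.4.2.1.1 to 10.4.2.1.4, for attendance, activities, spirituality and barriers. What is missing is any combination of those effects with a mediator-to-outcome effect.
- The hypotheses are framed irrespective of arm, so an a·b product answers a related but different question. It is needed only if mediation of the treatment effect is claimed.
- The causal sentence appears only in 10.4.3.1.1; 10.4.3.1.4 says merely that the null hypothesis will be evaluated.
- Same-window timing is inferred from identical visits and the absence of a lag. Sections 3.8 and 5.4.3 show that a time order was intended, and figures in 10.4.3 are not shown.
- Section 5.4.3 calls this work exploratory, and 10.4 does not list mediation among its key secondary endpoints.

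These points limit the size of the concern without removing it. The protocol itself fixes the test and its causal reading, so this is not detail left to an SAP. Adding the main effect does not cure the trend-level confounding, and it makes the test nearly blind to a constant effect. No analysis choice can supply a missing SUSS measurement.

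**Conclusion.** The concern holds on two counts.

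First, the rule in 10.4.3.1.1 estimates an association and cannot support the causal reading attached to it. A significant negative coefficient can arise from reverse causation or a shared factor with no mediation. There is no single false-positive rate to quote. For plain same-window correlation the rate is high without a mediator main effect and about nominal with it. For a factor driving both trends it is inflated either way: 15% to 100% with the main effect in the table above, and 12% to 98% in a second set of runs. All strengths are assumptions, so the figures are illustrative.

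Second, 10.4.3.1.4 cannot be tested as written, because change in disease-model endorsement is never measured. This rests on the SUSS being the only participant instrument described with that subscale.

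It would be wrong to infer that the trial's main result is at risk. The primary analysis does not use the mediators.

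**What to change.** **Attendance and activities.** Model use in window k on the mediator in window k−1, with the mediator main effect in the model, adjusting for arm, earlier use, site and court mandate. Daily attendance on the Substance Use Calendar already allows this. If mediation of the STAGE-12 effect is to be claimed, combine this effect with the arm-to-mediator effects planned in 10.4.2 and report the indirect effect with a bootstrap interval.

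**Spirituality and barriers.** With measurements only at baseline and week 8, a window-by-window lag is impossible. Use change from baseline to week 8 to predict attendance and involvement after week 8 only. Reconcile the SYRAAP schedule in 5.4.3.2.3 with Table 1.

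**Interpretation.** Replace the causal verb in 10.4.3.1.1 with wording of association. Lagging sets the order in time but does not remove unmeasured confounding.

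**Hypothesis 10.4.3.1.4.** Add the SUSS, a 5-minute computer-administered form, at the existing week-8 visit. Otherwise delete the hypothesis or restate it as prediction from the baseline score.

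**Cost.** More analysis work, loss of the first window as an outcome in the lagged models, and at most one short form at one visit. The minimum is to soften the causal wording and drop or restate 10.4.3.1.4.

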10.4.3.1.2 Hypothesis

Increases in 12-step meeting attendance and involvement, regardless of treatment condition, are mediated by increases in spirituality.

[figure not shown]
10.4.3.1.3 Hypothesis

Increases in 12-step meeting attendance and involvement, regardless of treatment condition, are mediated by decreases in 12-step ambivalence.

10.4.3.1.4 Hypothesis

Increases in 12-step meeting attendance and involvement, regardless of treatment condition, are mediated by increases in disease model endorsement.

The outcome variable will be percent of days (frequency) of the behaviors addressed in the SUC, SHAQ, and ITSI over the assessment window, measured baseline, weeks 4, 8/end of treatment, 3 months and 6 months. Each of the above hypotheses will be investigated by adding an interaction term time*Mediator to the hierarchical linear model, where Mediator denotes the factor of interest. Let γ_M denote the model coefficient associated with the time*Mediator term. The hypothesis H₀: γ_M =0 vs. H₁: $\gamma_M \neq 0$ will be evaluated.

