5.4.3.1.3 Addiction Severity Index – Lite, CTN Version

The ASI, developed by McLellan et al. (McLellan, Kushner et al. 1992) is a standardized, multidimensional, semi-structured interview that provides clinical information important for formulating treatment plans as well as problem severity profiles in six domains commonly affected in substance abusers. The domains covered are substance abuse (alcohol and drug), medical, psychiatric, legal, family/social and employment/support. Individuals are asked to indicate the number of days that they have experienced certain behaviors, emotions, or circumstances. A modified, shortened version of the ASI (CTN-ASI Lite) has been developed for use in the CTN; it includes only those questions used to derive the composite scores along with some demographic information. This version will be administered at baseline. The follow-up version of the CTN-ASI Lite uses a subset of the items in each of the domains; it will be administered at the 3 and 6-month follow-ups.

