10.4.1.1.3 Hypothesis

STAGE-12 will result in lower scores on the ASI Drug and Alcohol Composite Scores than TAU.

The outcome variable will be ASI Drug and Alcohol Composite Scores assessed at baseline, week 8/end of treatment, 3 months and 6 months. The data will be analyzed using a hierarchical linear model similar to the model for the primary outcome. Let α_S denote the effect of the STAGE-12 treatment in the Level-2 model. The hypotheses H₀: α_S =0 vs. H₁: α_S ≠0 will be evaluated and rejection of the null hypothesis with α_S < 0 would indicate that STAGE-12 treatment results in lower ASI Drug and Alcohol Composite Scores than TAU.

10.4.2 12-Step Outcomes

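### The disease-model mediation hypothesis (10.4.3.1.4) needs a change score that the schedule never collects; the ASI times in 10.4.1.1.3 and the ITSI outcome also conflict with the schedule

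*Protocol*

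**What the plan says.** **Disease model.** Section 10.4.3.1.4 states: "Increases in 12-step meeting attendance and involvement, regardless of treatment condition, are mediated by increases in disease model endorsement". The construct comes from the SUSS, of which section 5.4.3.4.1 says: "Three factor analytically derived subscales have been identified: disease model, psychosocial model, and eclectic orientation". On timing, the same section says "This scale will be collected at baseline". The participant SUSS row in Table 1 is marked at baseline and nowhere else.

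**ITSI.** The outcome for the three attitude-mediation hypotheses (10.4.3.1.2 to 10.4.3.1.4) is the frequency of "the behaviors addressed in the SUC, SHAQ, and ITSI over the assessment window".

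**ASI.** Section 10.4.1.1.3 defines the outcome as "ASI Drug and Alcohol Composite Scores assessed at baseline, week 8/end of treatment, 3 months and 6 months". Section 5.4.3.1.3 gives the baseline version at baseline and says of the follow-up version that "it will be administered at the 3 and 6-month follow-ups". Table 1 agrees with section 5.4.3.1.3. The composites are the last item on the key secondary list in section 10.4.

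**Spirituality and perceived barriers.** Section 10.4.2.1.3 uses the "Spiritual Involvement and Beliefs Scale at baseline and week 8/end of treatment", and section 10.4.2.1.4 uses the Perceived Barriers subscale of the SYRAAP at the same two times. Both call for a hierarchical model like that of section 10.3.1. That model indexes its responses by post-baseline assessment and gives each participant a random intercept, a random slope and a residual. Section 5.4.3.2.3 mentions the SYRAAP at baseline only, whereas Table 1 marks baseline and week 8.

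**The concern.** An analysis section that asks for measurements the schedule does not contain cannot be carried out as written. Where the mismatch is an extra time point or a stray name, the analyst has to decide after data collection what was meant. Where the missing item is the mediator itself, no analysis text can repair it, because there is no follow-up value to analyse. At stake is one pre-specified hypothesis serving the secondary objective on client attitudes and beliefs as mediators, together with clear definitions for the ASI endpoint, the attitude-mediation outcomes and two 12-step belief outcomes.

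**Working it through.** The plan states no figure to reproduce here. The check sets section 10.4 beside section 5.4 and Table 1, and then asks what the section 10.3.1 model can estimate from the values collected.

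**Step 1. Times analysed against times collected**

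| Analysis | Needed | Collected |
|---|---|---|
| 10.4.3.1.4 disease model (SUSS) | baseline and at least one later value | baseline only; 0 post-baseline |
| 10.4.1.1.3 ASI composites | baseline, week 8, 3 and 6 months | baseline, 3 and 6 months; 2 of 3 post-baseline |
| 10.4.3.1.2 to 10.4.3.1.4 outcome | SUC, SHAQ, ITSI | SUC and SHAQ at every listed time; ITSI absent from the abbreviations, Table 1 and section 5.4 |
| 10.4.2.1.3 spirituality | baseline, week 8 | baseline, week 8 |
| 10.4.2.1.4 perceived barriers | baseline, week 8 | baseline, week 8 in Table 1; baseline only in section 5.4.3.2.3 |

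**Step 2. Disease-model change.** An increase is the SUSS score at a later time minus the SUSS score at baseline. With no later score the quantity does not exist for any participant in either arm.

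**Step 3. ASI without week 8.** Take 3 and 6 months as weeks 13 and 26, as section 10.6 does. Write s0 for the random-intercept variance, sb for the random-slope variance and se for an independent, equal-variance residual. Post-baseline data give three moments:
- variance at week 13 = s0 + 169 sb + se
- variance at week 26 = s0 + 676 sb + se
- covariance = s0 + 338 sb

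The two variances differ by 507 sb, which fixes sb; the covariance then fixes s0, and either variance fixes se. Three parameters rest on three moments (rank 3), so the model can be fitted without week 8.

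**Step 4. Spirituality and perceived barriers.** With week 8 as the only response there is one moment:
- variance at week 8 = s0 + 64 sb + se

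That is one equation for three unknowns (rank 1 of 3). The fixed part is also redundant. With 10 sites (section 5.2) there are 10 site intercepts, 10 site slopes, the arm-by-time term and court mandate, 22 columns in all. At a single time each site-slope column is 8 times its site-intercept column, so 10 columns are redundant and the rank is 22 - 10 = 12. The arm coefficient remains estimable: it is the adjusted week 8 difference divided by 8.

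If baseline enters as a response at time 0, there are three moments: s0 + se, s0 + 64 sb + se, and covariance s0. The model is then just identified (3 parameters, rank 3) under an independent, equal-variance residual. With an unstructured residual matrix it is not (5 parameters, rank 3). That last failure is not peculiar to these scales: random effects plus an unstructured residual also exceed the moments for the four post-baseline times of the primary outcome (12 parameters, rank 10).

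**Step 5. Count.** Sections 10.4.1, 10.4.2 and 10.4.3 contain 3 + 4 + 4 = 11 hypotheses. Taking Table 1 as the governing schedule, the only one whose required data are absent is 10.4.3.1.4.

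**The case against.** The strongest reply is that little is lost. The mediation test is a time-by-mediator term, which can be computed with the baseline SUSS. Section 10.4 treats any significant secondary finding as exploratory. The mediation, spirituality and barriers hypotheses are not on its key list, and the ASI is last on it. A separate analysis plan may settle model details.

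Much of this stands, but it does not rescue the disease-model hypothesis. A term built on the baseline SUSS asks whether initial belief predicts the later trajectory. The hypothesis concerns a rise in belief, and an analysis plan cannot supply a measurement that was never taken.

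The reply does limit the rest. A reader might infer that four of the 11 hypotheses lack data or an estimable model. The documents do not support that:
- The ASI section names one time too many, and the model still fits with the two post-baseline values collected.
- Table 1 supplies both times named for spirituality and perceived barriers. Those sections ask only for a model resembling the primary one, and the arm contrast they test is estimable. What fails, on post-baseline data alone, is the separation of the variance components.
- The three hypotheses that mention the ITSI keep their SUC and SHAQ outcomes.

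**Conclusion.** The point holds, at moderate weight. One of 11 hypotheses (disease-model change) lacks its data and cannot be tested as written. The ASI times and the ITSI are contradictions within the protocol that text can correct without loss of an endpoint. For spirituality and perceived barriers the model does not suit the data, which is a milder matter. The primary analysis is unaffected.

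The count assumes that Table 1, not section 5.4.3.2.3, governs the SYRAAP. If sites followed section 5.4.3.2.3 and gave it at baseline only, perceived barriers would have no post-baseline value and 10.4.2.1.4 would fail for the same reason as the disease-model hypothesis. The statement that the ASI model fits assumes an independent, equal-variance residual.

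**What to change.** - **10.4.3.1.4:** restate the hypothesis as baseline disease-model endorsement predicting 12-step attendance and involvement. The alternative is to give the SUSS (5 minutes, computer-administered) at the existing week 8 visit in both arms. That keeps the change hypothesis, but it alters data collection at about 10 sites, needs an amendment approved before use (section 7.1), and adds to the assessment burden that section 5.4 sets out to limit.
- **10.4.3.1.4, outcome sentence:** delete ITSI; the SUC and SHAQ supply the outcome.
- **10.4.1.1.3:** change the ASI times to baseline, 3 months and 6 months.
- **10.4.2.1.3 and 10.4.2.1.4:** specify an ANCOVA of the week 8 score on arm, adjusted for the baseline score, site and court-mandate status.
- **5.4.3.2.3:** reconcile the SYRAAP times with Table 1 and section 10.4.2.1.4.

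Apart from the optional SUSS at week 8, these are text corrections that require no new data.
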